11.5.3. Safety

Laboratory Parameters

- If a laboratory value, which is expected to have a numeric value for summary purposes, has a non-detectable level reported in the database, where the numeric value is missing, but typically a character value starting with '<x' or '>x' (or indicated as less than x or greater than x in the comment field) is present, the number of significant digits in the observed values will be used to determine how much to add or subtract in order to impute the corresponding numeric value.
 - Example 1: 2 Significant Digits = '< x ' becomes x - 0.01
 - Example 2: 1 Significant Digit = '> x' becomes x + 0.1
 - Example 3: 0 Significant Digits = '< x' becomes x - 1.
- If there is more than one value of a particular parameter for a subject for a visit, the last assessment will be used in summary; all values will be listed.

11.5.4. Efficacy

Calculation of Time to Delivery

- Once delivery is confirmed, the maternal delivery and hospitalization records will be reviewed for data collection by the investigator obstetrician. The time to delivery is calculated as the days between the delivery and start time of the infusion of IP using the formula below:

$$\text{Time to delivery (days)} = (\text{date/time of delivery} - \text{date/time of start of infusion}) / (24*60)$$
The exact date/time of delivery and infusion will be used to determine the time to delivery.
- Time to delivery or retreatment/subsequent preterm labor is defined as the days between start time of the infusion of IP and the first occurrence among delivery, retreatment and subsequent preterm labor in a similar fashion to the time to delivery.

Calculation of Neonatal Composite Endpoint

Neonatal Composite Endpoint

The presence of any of the following endpoints determined from review of medical records will lead to a value of 1 for the neonatal composite endpoint and 0 otherwise:

- Fetal or neonatal death
- Respiratory Distress Syndrome (RDS)
 - Requiring continuous positive airway pressure or mechanical ventilation. Diagnosis requires a chest radiograph consistent with RDS (reticulogranular appearance to the lung fields or air bronchograms) within the first 24 hours of life

OR

- Received surfactant for a clinical picture of RDS within the first 24 hours of life
- Bronchopulmonary dysplasia at ≥ 36 weeks postmenstrual age (determined by adding chronological age to GA at delivery), defined as follows:
 - >21% supplemental oxygen requirement

OR

- Use of high flow nasal cannula at ≥ 1 L (21% oxygen)
- Necrotizing enterocolitis or isolated perforation
 - Diagnosed by radiographic evidence of Stage II or higher according to Bell's staging criteria (fixed/unchanging bowel loops, pneumatosis intestinalis, portal venous gas, pneumoperitoneum)

OR

- Pneumatosis intestinalis, bowel necrosis, or perforation noted at surgery
- Sepsis based on positive blood culture with clinical features of sepsis
- Meningitis based on positive cerebrospinal fluid culture performed as part of infection workup
- Retinopathy of prematurity
 - Confirmed by an ophthalmologist based on international committee Stage 4 or 5

OR

- Requiring surgical treatment with laser or other surgical intervention including cryotherapy or treatment with anti-VEGF (vascular endothelial growth factor)
- Intraventricular Hemorrhage (IVH)
 - Grade 3 or 4 (severe IVH)

OR

- Any grade of IVH with posthemorrhagic hydrocephalus requiring a shunt
- White matter injury, documented on cranial ultrasound or magnetic resonance imaging, as indicated by the following:
 - Multiple cystic lucencies in periventricular white matter (may be bilateral or unilateral, may vary in size, and be diffuse or focal in distribution)

OR

- Porencephalic cyst (not including subependymal or choroid plexus cysts)

OR

- Persistent ventriculomegaly, moderate to severe
- Cerebellar hemorrhage (unilateral or bilateral)

Individual Neonatal Composite Endpoint

- This will be derived for all the conditions included under the composite endpoint. For each individual condition, the variable will be 1 if the condition is satisfied, otherwise, 0.

Neonatal Composite Endpoint without RDS

- Same as the composite endpoint without the RDS condition.

Neonatal Composite Endpoint without RDS and mortality

- Same as the composite endpoint without the RDS and fetal/neonatal death conditions.

Modified Neonatal Composite Endpoint

- Same as the composite endpoint and include the all reported neonatal events. For example, a subject is considered as experience a RDS even without record of CPAP, ventilation or Surfactant. .

Calculation of Gestational Age at Birth and Proportion of Pre-term Births

- Gestational age at birth (weeks) is defined as the gestational age when the baby is born and is captured in the eCRF. If the data are missing, the GA at birth can be calculated as follows:

$$\text{GA at Birth (weeks)} = (\text{GA at Randomization} \times 7 + \text{Time to delivery}) / 7$$

GA at randomization will be converted to 1 decimal place (i.e. 30.2 weeks GA at randomization) prior the calculation.

- Proportion of births prior to $37^{0/7}$, $35^{0/7}$, $32^{0/7}$, or $28^{0/7}$ week's gestation (preterm)

Subjects are considered to have delivered prior to $37^{0/7}$ weeks if the gestational age at birth is less than $37^{0/7}$ weeks (e.g.: < 37.0 weeks). Other proportions also will be calculated in a similar fashion. For proportion of births prior to $32^{0/7}$ and $28^{0/7}$ week's gestation, only mothers who were randomized prior to $32^{0/7}$ and $28^{0/7}$ week's gestation will be included respectively.

- Proportion of births at term ($\geq 37^{0/7}$ week's gestation)

Subjects are considered to have delivered at term if the gestational age is $\geq 37^{0/7}$ (e.g., ≥ 37.0 weeks)

Calculation of Neonatal Hospital Admission

- For the delivery visit hospitalization, the length of the hospital stay (days) and associated hospital unit (NICU, nursery level, or level of care 1 to 4) will be recorded. The length of stay is calculated as the days between the delivery date/time and discharge date/time.
- In addition, whether the baby was transported to a different hospital or extended stay facility and length of stay (days) and number of hospital readmissions in the month following discharge from the delivery visit hospitalization will also be captured and reported.

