4. ANALYSIS POPULATIONS

Population	Definition / Criteria	Analyses Evaluated
All Randomized	
 • Consists of all mothers randomly assigned to treatment regardless of whether they actually are treated. • Subjects will be presented by their planned randomized treatment 	
 • Subject Disposition
Randomized but not dosed	
 • Consists of all mothers that are randomized but fail to receive any study treatment. • Subjects will be presented by their planned randomized treatment. 	
 • Subject Disposition
Maternal Safety	
 • Mothers randomly assigned to treatment who have been exposed to study treatment. • Randomly assigned subjects will only be excluded if there is clear evidence the subject did not receive IP. • Subjects will be analyzed according to their actual treatment. Any subject who received both treatments (retosiban and atosiban) will be assigned to retosiban group for actual treatment. 	
 • Maternal and fetal safety
Neonatal Safety	
 • Consists of neonates whose mothers received randomized treatment. • Subjects are analyzed according to the actual treatment their mothers received. • Any subject who received both treatments (retosiban and atosiban) will be assigned to retosiban group for actual treatment. 	
 • Neonatal safety
Maternal ITT	
 • Consists of all mothers randomly assigned to treatment who have been exposed to study treatment irrespective of their compliance to the planned course of treatment. • Subjects who are randomly assigned but fail to receive any study treatment will be presented separately. 	
 • Maternal and fetal efficacy endpoints
Neonatal ITT	
 • Dataset comprises all neonates whose mothers are the randomized Subjects who have been exposed to study drug, i.e., mothers from the ITT Population. 	
 • Neonatal efficacy endpoints

NOTE :

- Please refer to Section 11.11 Appendix 11: List of Data Displays which details the population to be used for each display being generated.

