8. SECONDARY AND EXPLORATORY ANALYSES

8.1. Secondary Efficacy Analyses

8.1.1. Overview of Planned Efficacy Analyses

The secondary efficacy analyses will be based on the Maternal and Neonatal ITT Populations.

Table 4 provides an overview of the planned efficacy analyses with further details of data displays presented in Appendix 11: List of Data Displays.

Table 4 Overview of Planned Efficacy Analyses

	Stats Analysis			Summary		Individual	
	T	F	L	T	F	F	L
Key Secondary Endpoints							
Proportion of births prior to 37 ^{0/7} weeks' gestation – ascertain the GA at delivery based on a records review	Y			Y			
Proportion of births at term (37 ^{0/7} to 41 ^{6/7} weeks' gestation) – ascertain the GA at delivery based on a records review	Y			Y			
Length of neonatal hospital stay – duration (in days) of neonatal hospital admission from the medical records	Y			Y			Y
Neonatal composite endpoint	Y			Y			Y
Other Secondary Endpoints							
Individual neonatal composite endpoint				Y			Y
Neonatal composite endpoint without RDS	Y			Y			Y
Neonatal composite endpoint without RDS and mortality	Y			Y			Y
Neonatal admission to a specialized				Y			Y

	Stats Analysis			Summary		Individual	
	T	F	L	T	F	F	L
care unit and length of stay							
Newborn hospital readmission and length of stay				Y			Y
Proportion of births prior to 28 ^{0/7} weeks' gestation	Y			Y			
Proportion of births prior to 32 ^{0/7} weeks' gestation	Y			Y			
Proportion of births prior to 35 ^{0/7} weeks' gestation	Y			Y			
Proportion of births ≤7 days of IP administration	Y			Y			
Proportion of births ≤48 hours of IP administration	Y			Y			
Proportion of births ≤24 hours of IP administration	Y			Y			

NOTES :

- T = Table, F = Figure, L = Listing, Y = Yes display generated.
- Stats Analysis = Represents TFL related to any formal statistical analyses (i.e. modelling) conducted.
- Summary = Represents TF related to any summaries (i.e. descriptive statistics) of the observed raw data.
- Individual = Represents FL related to any displays of individual subject observed raw data.

1. Will be presented in the integrated analysis.

Following review of the data, additional analyses maybe conducted to further support the evaluation and interpretation of the data.

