
 For binary endpoints, the number and percentage of subjects in each treatment group, the relative risk (RR) and 95% CIs, the odds ratio (OR) of response rates (retosiban versus atosiban) and 95% CIs, and p-value will be presented. The model-adjusted length of stay will be presented for each treatment group. In addition, the treatment difference between retosiban and atosiban and associated 95% CIs and p-values will be presented. Observed values using descriptive statistics for length of stay will be presented for each treatment group. For proportion of neonates with any of the composite component, neonates with any of the composite component w/o RDS, neonates with any of the composite component w/o RDS and mortality, and individual composite component, RR and 95% CIs, OR and 95% CIs, and p-values will be provided. 	
Sensitivity and Support Statistical Analysis	

 For length of stay, data will be analyzed in a similar fashion as described in Section 7.1.2. 	

Key Secondary Efficacy Statistical Analysis

- Treatment effects within defined subgroups in Section 5.1 will be explored.

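### The composite without RDS and mortality, and the single morbidities, score a death before diagnosis as no event, which tilts these supportive comparisons towards the arm with more early deaths

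*SAP*

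**What the plan says.** SAP 11.5.4 sets the base rule: any listed condition "will lead to a value of 1 for the neonatal composite endpoint and 0 otherwise". For the single components, "For each individual condition, the variable will be 1 if the condition is satisfied, otherwise, 0". Two reduced versions follow. One drops only RDS ("Same as the composite endpoint without the RDS condition") and so keeps death as an event. The other drops death as well ("Same as the composite endpoint without the RDS and fetal/neonatal death conditions").

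The analysis set in SAP Section 4 is the Neonatal ITT population: "Dataset comprises all neonates whose mothers are the randomized Subjects who have been exposed to study drug". It carries no condition on survival. One component has a minimum age built into its definition: "Bronchopulmonary dysplasia at ≥ 36 weeks postmenstrual age".

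The SAP is not consistent about which of these are formally compared. Table 4 in SAP 8.1.1 marks "Neonatal composite endpoint without RDS and mortality" for formal statistical analysis but marks the individual components as summary only. SAP 8.1.2, under Model Results Presentation, promises for "neonates with any of the composite component w/o RDS and mortality, and individual composite component, RR and 95% CIs, OR and 95% CIs, and p-values". SAP 8.1.3 lists the individual components among endpoints to be modelled like the composite. The version without RDS and mortality is not in the protocol's list of other secondary endpoints (Protocol 6.2.5), nor in the endpoint lists of SAP 2.2 and 8.1.3.

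**The concern.** Death prevents a later diagnosis and is worse than any of the morbidities it prevents. An infant who dies in the first days has no BPD, retinopathy or white matter injury on record, and under the rule above gets a 0 for each, as a healthy term baby does. The main composite avoids this by counting death as an event. The version without RDS and mortality and the single morbidities do not.

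When early deaths are unequal between arms, the arm with more of them therefore tends to show lower morbidity. This matters because Protocol 1.3.1 (Table 1) names adverse fetal and neonatal outcomes from prolonging pregnancy in subclinical intrauterine infection as a potential risk. A morbidity comparison that can improve when infants die is a poor guide to that risk if read on its own.

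**Working it through.** **Step 1: apply the rule to a death before any non-RDS morbidity is diagnosed.**

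| Endpoint | Score |
|---|---|
| Full composite | 1 (through death) |
| Composite without RDS | 1 (through death) |
| Death as a single component | 1 |
| Composite without RDS and mortality | 0 |
| Each single morbidity not yet diagnosed | 0 |

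A morbidity diagnosed before death still scores 1, so only deaths before diagnosis are affected.

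**Step 2: look for a rule that repairs this.**
- Imputation in SAP 11.7.2 replaces missing composite scores. Under the 1/0 rule a death gives 0, which is not missing.
- The SAP restricts denominators elsewhere in 11.5.4: births before 32 and before 28 weeks count only mothers randomized before those ages. There is no matching restriction for morbidities.
- BPD needs survival to 36 weeks postmenstrual age. An infant born at 24 weeks, the earliest gestation at entry, must survive 36 − 24 = 12 weeks before BPD can be scored.

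**Step 3: size.** The plan states no figure to reproduce. Inputs:
- n = 48 per arm, about half of the 97 randomized 1:1 (SAP 2.3). Neonatal ITT counts only neonates of dosed mothers, so 48 is approximate.
- q = morbidity risk among infants alive to be diagnosed, equal in both arms, so the true odds ratio is 1.00. Assumed 10%, 20% and 30%.
- d = deaths before diagnosis. Assumed 0 in one arm and 2 or 4 in the other.

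Formulas, using expected counts:
- SAP rule: rate = q(n − d)/n
- Death counted as an event: rate = [q(n − d) + d]/n
- Odds ratio = odds in the arm with deaths ÷ odds in the arm without

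Worked case, q = 20%, 4 versus 0 deaths:
- SAP rule: 0.20 × 44/48 = 18.3% versus 20.0%; OR = (0.183/0.817)/(0.200/0.800) = 0.90.
- Death as an event: (0.20 × 44 + 4)/48 = 26.7% versus 20.0%; OR = 1.45.

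| Deaths | q | OR, SAP rule | OR, death as an event |
|---|---|---|---|
| 2 v 0 | 10% | 0.95 | 1.43 |
| 2 v 0 | 20% | 0.95 | 1.22 |
| 2 v 0 | 30% | 0.94 | 1.14 |
| 4 v 0 | 10% | 0.91 | 1.91 |
| 4 v 0 | 20% | 0.90 | 1.45 |
| 4 v 0 | 30% | 0.89 | 1.30 |
| 2 v 2 | any of the three | 1.00 | 1.00 |

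Shift per death under the SAP rule = q/n: 0.10/48 = 0.2 percentage points, 0.20/48 = 0.4, 0.30/48 = 0.6.

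**The case against.** **Death is reported elsewhere.** A reader might infer that the rule hides a mortality harm. The documents do not support that. Death is an event in the key secondary composite and in the composite without RDS, and it is a component in its own right. Neonatal death and intrauterine fetal demise are AESIs (SAP 8.2.3.6), tabulated by arm in Tables 3.171 and 3.271, and neonatal deaths are in Listing 97. This stands: the fault is confined to supportive endpoints.

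**The effect is small.** A reader might infer that each early death moves the rate by a full 1/48 = 2.1 points, or build a case with five diseased infants per arm of whom two die undiagnosed in one arm: 3/48 versus 5/48, OR (3/45)/(5/43) = 0.57, RR 0.60. Both assume that every infant who dies would have been diagnosed. That is the upper limit, and nothing in the documents places it as the likely case.

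**Not all components are equally exposed.** RDS is assessed in the first 24 hours. Sepsis, meningitis, necrotizing enterocolitis and IVH can be diagnosed at any time before death. Only BPD has a stated minimum age. This stands too.

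**Stillbirth is uncertain.** It is tempting to say that a stillborn fetus is scored 0. Neonatal ITT is worded in terms of neonates; inclusion of fetal deaths is an inference from fetal death being a component analysed in that set.

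**Formal status is weak.** Besides the conflict over single components, the version without RDS and mortality has no titled table in SAP 11.11.3, although it may sit inside Table 2.101. With early termination and no multiplicity adjustment (SAP 5.2), its p-value would carry no confirmatory claim.

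None of this changes the direction of the error when early deaths are unequal.

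**Conclusion.** The point holds for the composite without RDS and mortality and for single morbidities that death can pre-empt, with BPD the clearest case. As written, a death before diagnosis is scored as absence of disease, and unequal early deaths move the comparison in favour of the arm with more of them.

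On the assumptions above, the odds ratio is 0.95 to 0.89 against a true 1.00, or about 0.2 to 0.6 percentage points per death. With equal deaths there is no distortion. These are illustrations, since the documents give no death or morbidity rates.

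The key secondary composite and the composite without RDS are sound on this point. A reader might infer that the affected endpoints must be deleted or replaced; that is not needed. The single components are protocol endpoints, and a breakdown without mortality is a legitimate description of what drives the composite. The correction is worth making because a stated rule gives a wrong-direction comparison and the remedy is cheap.

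**What to change.** In SAP 11.5.4, 8.1.1 (Table 4) and 8.1.2:

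1. Keep the protocol's single-component counts.
2. For BPD, make BPD or death before 36 weeks postmenstrual age the between-arm comparison.
3. For the other components and for the version without RDS and mortality, show the number of deaths without the diagnosis, by arm, in the same table.
4. Report the version without RDS and mortality descriptively, without a p-value. Leave the protocol's composite excluding RDS, which keeps death, as the compared measure.
5. Reconcile Table 4 with SAP 8.1.2 on whether single components are summarized only or also tested.
6. State whether fetal deaths are in the Neonatal ITT denominator.
7. Label any survivors-only rate as supportive, because it conditions on an outcome after randomization.

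The cost is SAP wording, a few derivation lines and one extra row per table. No protocol endpoint is lost.

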6.3. Demographic and Baseline Characteristics

For mothers, continuous variables, such as age (years), weight (kg), height (cm), BMI (kg/m²), gestational age at randomization (weeks/day), contraction frequency, cervical

dilation (cm), cervical length (mm), percentage of women who failed PTL criteria (inclusion criteria #4), fFN (continuous) and other baseline characteristics as needed will be summarized using descriptive statistics by treatment group. Since only year of birth is collected and the month and day of birth are not collected, a mother's age will be calculated using below algorithm.

- The day and month is imputed as '30th June'.
- The age of mother is calculated as the difference of the date of the first study treatment and the date of birth divided by 365.25. For example, if the date of the randomization was at 00:00 am on 20 March 2015 and date of birth was 1987, the age is 27.
- If no inclusion deviation in age requirement, the age is between 12 and 45 year old based on study entry criteria.
- The mother is recorded as an adolescent in CRF if she is adolescent (12 to < 18 years of age), so age will be adjusted. For example, the calculated age is 18.2 but a subject is marked as an adolescent in CRF, a subject's age is to 18.

GA at randomization in weeks/days will be obtained from CRF and will be converted into numeric value as covariate in the statistical analysis of primary and secondary endpoint. Please refer to Appendix 11.6.2 for missing GA at randomization.

The following categorical variables will be summarized by reporting the number and percentage of subjects in each category by treatment group:

- Race
- Ethnicity
- GA at randomization (4 GA strata: $24^{0/7}$ to $25^{6/7}$, $26^{0/7}$ to $27^{6/7}$, $28^{0/7}$ to $30^{6/7}$ and $31^{0/7}$ to $33^{6/7}$)
- Established progesterone use
- Region
- Prior tocolytic use in current episode (Beta-mimetics, Magnesium Sulfate, Calcium channel Blockers, NSAIDs, and Oxytocin receptor antagonists)
- Adolescent (between 12-<18 years) and adult (≥ 18 years) patients.
- fFN (positive or negative)

For fetus, continuous variables, such as estimated weight (g) and AFI results (cm) measured using the 4-quadrant method will be summarized.

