11.6.2.1. Handling of Missing Stratification

Element	Reporting Detail
GA at Randomization	
 If GA at randomization in weeks/days obtained from CRF is missing, the upper bound of the GA strata assigned at randomization will be used as a numeric value. For example, a subject in 24^{0/7} to 25^{6/7} group, 25 weeks and 6 days will be converted into numeric value.
Established Progesterone Use	
 Established progesterone use will be derived using medications which are taken prior to the study treatment and recorded in obstetrical medications CRF page. If a subject is stratified as progesterone user at the randomization but no progesterone medication prior to the study treatment was recorded in obstetrical medications CRF page, the subject will be considered as established progesterone user for analysis.

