11.6.2.2. Handling of Missing/Partial Dates

Element	Reporting Detail
---------	------------------

Element	Reporting Detail				
General	Partial dates will be displayed as captured in subject listing displays.				
Concomitant Medication	Partial start dates of prior and concomitant medications will be assumed to be the earliest possible date consistent with the partial date. In the case of a missing year, the year will be assumed to be the year part of informed consent date of that subject. In the case of a completely missing start date, the start date will be assumed to be prior to date of the first administration of study medication. Partial stop dates of prior and concomitant medications will be assumed to be the latest possible date consistent with the partial date. In the case of a completely missing stop date, the medication will be assumed to be ongoing.				
Time to Delivery	
For the delivery date/time of the primary endpoint,
 
 Missing data with respect to time to delivery endpoint is unlikely to occur. If it occurs and the dates are missing, the last assessment date of a mother prior to delivery phase will be used. If the times are missing, a "00:00" will be used for the time. 				
Adverse Events (General)	
 If the dates are missing for on-treatment, or post-treatment AEs, imputation of AE dates may be performed if needed. The eCRF allows for the possibility of partial dates (i.e., only month and year) to be recorded for AE start and end dates; that is, the day of the month may be missing. Start or end dates which are completely missing (i.e. no year specified) will remain missing, with no imputation applied. There will be no imputation for AE data listings 				

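### Three SAP missing-data fallbacks for gestational age and delivery time give one-sided or impossible values

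*SAP*

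**What the plan says.** **GA at birth (SAP 11.5.4).** The eCRF is the first source: "Gestational age at birth (weeks) is defined as the gestational age when the baby is born and is captured in the eCRF". The formula is a fallback: "If the data are missing, the GA at birth can be calculated as follows", namely (GA at randomization × 7 + time to delivery) / 7. Before it is applied, "GA at randomization will be converted to 1 decimal place (i.e. 30.2 weeks GA at randomization) prior the calculation". The SAP does not say which weeks and days the example 30.2 stands for. The result is compared with numeric cut-offs; for preterm birth the SAP gives "e.g.: < 37.0 weeks", and the 35-, 32- and 28-week cut-offs work the same way.

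**GA as a covariate (SAP 6.3).** "GA at randomization in weeks/days will be obtained from CRF and will be converted into numeric value as covariate". No conversion rule is given there.

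**Missing GA at randomization (SAP 11.6.2.1).** "the upper bound of the GA strata assigned at randomization will be used as a numeric value". The example puts a woman in the lowest stratum at 25 weeks 6 days.

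**Missing delivery time (SAP 11.6.2.2).** "If the times are missing", 00:00 is used. The same entry calls missing time-to-delivery data unlikely.

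**Worked example (SAP 7.1.2).** Infusion at 12:00 pm on 1 March 2015 and delivery at 00:00 on 20 March 2015 are said to give 19.5 days.

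**The concern.** A fallback value should be roughly central among the values that the missing item could have taken, and it should be possible. These three are not. The one-decimal example cannot come from ordinary rounding, and the ways of reaching it all lower GA. The top of the stratum can never be too low. Midnight can never be too late on the ordinary reading of the clock, and it can place delivery before the infusion started.

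The values feed endpoints that matter. Time to delivery is the primary endpoint. The proportions delivered within 24 hours, 48 hours and 7 days are secondary endpoints, and the primary mixture model pre-assigns deliveries within 1 week to its first component. GA at birth decides preterm or term status, both key secondary endpoints.

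**Working it through.** **1. The one-decimal conversion.** Inputs: the SAP 11.5.4 example and formula. Exact GA is weeks + days/7. Errors are in days, computed as (converted − exact) × 7.

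| GA | Exact | Nearest 0.1 (error) | Truncated (error) | Weeks.days (error) |
|---|---|---|---|---|
| 30w0d | 30.000 | 30.0 (0) | 30.0 (0) | 30.0 (0) |
| 30w1d | 30.143 | 30.1 (−0.3) | 30.1 (−0.3) | 30.1 (−0.3) |
| 30w2d | 30.286 | 30.3 (+0.1) | 30.2 (−0.6) | 30.2 (−0.6) |
| 30w3d | 30.429 | 30.4 (−0.2) | 30.4 (−0.2) | 30.3 (−0.9) |
| 30w4d | 30.571 | 30.6 (+0.2) | 30.5 (−0.5) | 30.4 (−1.2) |
| 30w5d | 30.714 | 30.7 (−0.1) | 30.7 (−0.1) | 30.5 (−1.5) |
| 30w6d | 30.857 | 30.9 (+0.3) | 30.8 (−0.4) | 30.6 (−1.8) |
| Mean error | | 0 | −0.3 | −0.9 |

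The SAP's 30.2 never appears under nearest rounding. It appears for 30w2d under truncation and under weeks.days.

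Effect at the 37-week cut-off:
- Entry at 30w2d is 212 days. Birth 47 days later is 259 days, exactly 37w0d (term). The formula gives (30.2 × 7 + 47)/7 = 258.4/7 = 36.91, scored preterm, under either reading.
- Entry at 30w6d with birth 44 days later is 260 days, 37w1d. Weeks.days gives (30.6 × 7 + 44)/7 = 36.89 (preterm). Truncation gives 37.09 and nearest rounding 37.19 (both term).
- Nearest rounding is not safe at the boundary either. Entry at 30w3d plus 46 days is 37w0d, but (30.4 × 7 + 46)/7 = 36.97.
- Removing the rounding alone is not enough, because the formula adds fractional elapsed time to a whole-day GA. Entry at 30w6d (216 days) with delivery 43 calendar days later but 42.75 elapsed days gives (216 + 42.75)/7 = 36.96, although the delivery date is 37w0d.

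**2. Top of stratum.** Inputs: the four GA strata, with GA assumed uniform over the days of each stratum.
- 2-week strata (14 days each): overshoot 0 to 13 days, mean 13/2 = 6.5.
- 3-week strata (21 days each): overshoot 0 to 20 days, mean 20/2 = 10.
- With the 1:2:4:8 enrollment mix assumed in Protocol 8.2.1: (1 × 6.5 + 2 × 6.5 + 4 × 10 + 8 × 10)/15 = 9.3 days.

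If GA at birth is missing as well, the overshoot passes straight into it through the formula.

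**3. Midnight.** With the delivery date known, the shift is minus the true time of day: from 0 to just under −1 day, mean about −0.5 if times are uniform over the day. Illustrations, all with infusion at 12:00:
- Same-day delivery, time missing: 00:00 − 12:00 = −0.5 day.
- Delivery at 18:00 next day: 30 hours, scored 12 hours (now ≤24 hours).
- Delivery at 18:00 two days later: 54 hours, scored 36 hours (now ≤48 hours).
- Delivery at 18:00 seven days later: 7.25 days, scored 6.5 (now ≤7 days, and in the group pre-assigned to the first mixture component).

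**4. The SAP 7.1.2 example.** From 12:00 on 1 March to 00:00 on 20 March is 18.5 days. The printed 19.5 follows only if 00:00 means the end of 20 March, or if the two clock times are swapped.

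**The case against.** The best defence is that these are rare, treatment-blind fallbacks. GA is both an eligibility criterion and a stratification factor, so a missing CRF value should be uncommon. The top-of-stratum value stays inside the assigned stratum, so GA subgroup membership does not change. Delivery date and time come from hospital records, and the midnight shift is under 1 day against a 9.5-day design difference. The stratum midpoint and midday are single imputations too. All of this stands, and it limits the importance of the point. It does not justify keeping values that are one-sided or impossible when central ones cost nothing more.

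A reader might also infer four stronger things that the documents do not support:
- *That 30.2 can only be 30 weeks 2 days written as a decimal.* Truncating 30 2/7 gives 30.2 as well, and the SAP does not say which is meant. The 1.8-day figure belongs to one reading only.
- *That the formula decides the GA cut-offs for everyone.* It is used only when the eCRF value is missing.
- *That the one-decimal rule distorts the GA covariate in the efficacy models.* The rule is tied to the GA-at-birth calculation. SAP 6.3 gives no conversion, which is a gap to close and not evidence that the wrong conversion will be used.
- *That the rules share a direction and so bias the comparison.* Top of stratum moves GA up, while the other two move values down, and none depends on arm. The 7.1.2 example, if its 00:00 means end of day, would even reverse the midnight shift.

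**Conclusion.** The point holds as a defect in three stated fallback rules. The conversion implied by the 30.2 example lowers GA by at most 0.6 or 1.8 days, depending on the reading, and can turn a birth at exactly 37w0d into a preterm one. The stratum upper bound is the largest shift: up to 13 or 20 days high, with a mean of 6.5 or 10 days if GA is uniform within strata. Midnight costs up to 1 day, about 0.5 on average if delivery times are uniform, and can give negative times or flip the short-interval endpoints.

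The number of women affected is not in the documents. The SAP calls missing time to delivery unlikely. The protocol's sample size allowed for 10% missing birth data, which for the 97 enrolled would be about 10 women (0.10 × 97 = 9.7) if that rate applied, but it is not a rate for missing GA or missing clock times. No distortion of the treatment comparison is shown. The case for changing the rules is that, when followed, they give wrong values that are easy to avoid.

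**What to change.** Before database freeze:
1. **GA.** Hold GA in whole days (weeks × 7 + days; in weeks, weeks + days/7 unrounded). For a missing GA at birth, add the calendar days from randomization to delivery, and apply the cut-offs in days (37w0d = 259). State the same conversion for the covariate in SAP 6.3, and delete the one-decimal sentence.
2. **Missing GA at randomization.** Derive it from the due date where recorded. The protocol fixes the due date at 40w0d, so GA in days = 280 − (due date − randomization date). Otherwise use the stratum midpoint.
3. **Missing delivery time.** Use 12:00. For delivery on the day of infusion, use the midpoint between infusion start and 23:59.
4. **Worked example in SAP 7.1.2.** Correct it to 18.5 days for the times stated.

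The cost is a few derivation lines and one corrected example. No new data are collected, and records with complete data keep their values.
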